7.1.1 Potential drug-induced liver injury IMP discontinuation criteria

Study participants with potential drug-induced liver injury (PDILI) must be assessed to determine if IMP must be discontinued. In addition, all concomitant medications and herbal supplements that are not medically necessary should also be discontinued.

The PDILI criteria below require immediate and permanent discontinuation of IMP for study participants with either of the following:

- ALT or AST $\geq 8 \times$ ULN
- ALT or AST $\geq 3 \times$ ULN and coexisting total bilirubin $\geq 2 \times$ ULN

The PDILI criterion below requires immediate discontinuation of IMP for:

- Study participants with ALT or AST $\geq 3 \times$ ULN who exhibit temporally associated symptoms of hepatitis or hypersensitivity. Hepatitis symptoms include fatigue, nausea, vomiting, and right upper quadrant pain or tenderness. Hypersensitivity symptoms may include fever (without clear alternative cause), rash, or eosinophilia (ie, $>5\%$).

If a nondrug-related cause for the symptoms can be confirmed, these study participants may resume IMP administration after discussion with the responsible UCB Study Physician, but only when the requirements for rechallenge with IMP as provided in Section 10.6.2.1 are followed.

The PDILI criterion below allows for study participants to continue on IMP at the discretion of the Investigator.

- Study participants with ALT or AST $\geq 5 \times \text{ULN}$ and $< 8 \times \text{ULN}$, total bilirubin $< 2 \times \text{ULN}$, and no eosinophilia (ie, $\leq 5\%$), with no fever, rash, or symptoms of hepatitis (eg, fatigue, nausea, vomiting, right upper quadrant pain or tenderness).

Evaluation of PDILI must be initiated as described in Section 10.6.3, with repeat tests performed in 2 weeks. Upon retest, if ALT or AST values have reduced to $< 5 \times \text{ULN}$, the study participant can continue with the study. However, if ALT or AST remains $\geq 5 \times \text{ULN}$ and $< 8 \times \text{ULN}$ after retest, IMP should be temporarily withheld and study participant should undergo a repeat test in two weeks. If ALT or AST values remain $\geq 5 \times \text{ULN}$ even after the second retest, then the study participant should be permanently withdrawn from the study and should be followed for possible drug-induced liver injury.

If study participants are unable to comply with the applicable monitoring schedule, IMP must be discontinued immediately.

Investigators should attempt to obtain information on study participants in the case of IMP discontinuation to complete the final evaluation. Study participants with PDILI should not be withdrawn from the study until investigation and monitoring are complete. All results of these evaluations and observations, as well as the reason(s) for IMP discontinuation and study participant withdrawal (if applicable), must be recorded in the source documents. The eCRF must document the primary reason for IMP discontinuation.

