ALT=alanine aminotransferase; AST=aspartate aminotransferase; BUN=blood urea nitrogen; eCRF=electronic Case Report Form; HBsAg=hepatitis B surface antigen; hCG=human chorionic gonadotropin; GGT=gamma glutamyltransferase; HIV=human immunodeficiency virus; IGRA= interferon-gamma release assay; INR=international normalized ratio; LDH=lactate dehydrogenase; MCH=mean corpuscular hemoglobin; MCHC=mean corpuscular hemoglobin concentration; MCV=mean corpuscular volume; RBC=red blood cell count; ULN=upper limit of normal; WBC=white blood cell count

^a Details of liver chemistry stopping criteria and required actions and follow-up assessments after liver stopping or monitoring event are given in Section 7.1.1 and Appendix 6 (Section 10.6). All events of ALT ≥3×ULN and bilirubin ≥2×ULN (>35% direct bilirubin) or ALT ≥3×ULN and INR >1.5, if INR measured, may indicate severe liver injury (possible Hy's Law) and must be reported as an SAE.

Investigators must document their review of each laboratory safety report.

Laboratory/analyte results that could unblind the study will not be reported to investigative sites or other blinded personnel until the study has been unblinded.

This document cannot be used to support any marketing authorization application and any extensions or variations thereof.

PUBLIC COPY

10.3 Appendix 3: AEs – definitions and procedures for recording, evaluating, follow up, and reporting

Definition of AE

AE definition

• An AE is any untoward medical occurrence in a patient or clinical study participant, temporally associated with the use of IMP, whether or not considered related to the IMP.• NOTE: An AE can therefore be any unfavorable and unintended sign (including an abnormal laboratory finding), symptom, or disease (new or exacerbated) temporally associated with the use of IMP.

Events meeting the AE definition

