10.6 Appendix 6: Liver safety – suggested actions and follow-up assessments

The PDILI IMP discontinuation criteria for this study are provided in Section 7.1.1, with the accompanying required follow-up investigation and monitoring detailed below. All PDILI events must be reported as an AE and reported to the study site and Sponsor within 24 hours of learning of their occurrence. Any PDILI event that meets the criterion for potential Hy's Law must be reported as an AE of special interest (see Section 8.2.8.6), and, if applicable, also reported as an SAE (see Section 8.2.8.4).

Evaluation of PDILI consists of the diagnostic testing and continued monitoring included in Table 10-3 (specific tests dependent on laboratory results and corresponding symptoms) and consultation with a local hepatologist (if applicable; discussed in Section 10.6.1). The local hepatologist is the expert usually consulted by the treating physician for assessment and management of potential hepatic disease. This would usually be a hepatologist, but may be a gastroenterologist. Additional investigation and monitoring may be required and adapted based on the diagnosis after the cause of the liver injury/abnormality is confirmed (details in Section 7.1.1.1).

The results of all monitoring, including laboratory testing and other testing, should be made available to the study site and Sponsor.

All initial tests resulting in abnormal hepatic laboratory values need to be repeated, but appropriate medical action must not be delayed waiting for the repeat result.

If tests are done locally for more rapid results, a concurrent sample should also be sent to the central laboratory whenever possible. Medical care decisions are to be made initially using the most rapidly available results, and a conservative approach must be taken if the results from the 2 laboratory tests are significantly different. Data from the local and central laboratory are to be recorded on the applicable eCRF pages.

When IMP is discontinued, all concomitant medications and herbal supplements that are not medically necessary should also be discontinued. In these cases, the Investigator should also consider dose reduction for medically necessary concomitant medication and consider changing any medically required concomitant medication known to be hepatotoxic to a suitable alternative.

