When IMP is stopped due to PDILI (as described in Section 7.1.1), IMP must be permanently discontinued unless a subsequent alternative diagnosis fully explains the hepatic findings. If a subsequent alternative diagnosis fully explains the hepatic findings, and the requirements provided in Section 10.6.2.1 are met, rechallenge with IMP may be appropriate.

Table 10-2 summarizes the approach to investigate PDILI.

Table 10-2: Required investigations and follow up for PDILI

Laboratory value			Immediate		Follow up	
ALT or AST	Total bilirubin	Symptoms ^a of hepatitis or hypersensitivity	Consultation requirements	Actions	Testing	Evaluation
≥3×ULN	≥2×ULN ^b	NA	Hepatology consult ^c Medical Monitor must be notified within 24 hours (eg, by laboratory alert) and study participant discussed with Medical Monitor ASAP.	Immediate IMP discontinuation. ^d	Essential: Must have repeat liver chemistry values and additional testing completed ASAP (see Section 10.6.3); recommended to occur at the site with HCP.	Monitoring of liver chemistry values at least twice per week until values normalize, stabilize, or return to within Baseline values. ^e
≥3×ULN	NA	Yes				
≥8×ULN	NA	NA	Need for hepatology consult to be discussed (required if ALT or AST ≥8×ULN) Medical Monitor must be notified within 24 hours (eg, by laboratory alert) and study participant discussed with Medical Monitor ASAP.			
≥5×ULN (and ≥2× Baseline) and <8×ULN	<2×ULN	No	Discussion with Medical Monitor required. Consider need for hepatology consult if there is no evidence of resolution (see	Further investigation – immediate IMP discontinuation not required (see Section 10.6.2).	Essential: Every attempt must be made to have repeat liver chemistry values and additional testing completed within 48 hours at the site with HCP (see Section 10.6.3).	Monitoring of liver chemistry values at least twice per week for 2 weeks. ^e • Immediate IMP discontinuation required if liver

Table 10-2: Required investigations and follow up for PDILI

Laboratory value			Immediate		Follow up	
ALT or AST	Total bilirubin	Symptoms ^a of hepatitis or hypersensitivity	Consultation requirements	Actions	Testing	Evaluation

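### Section 7.1.1 and Appendix 6 (Table 10-2) prescribe different actions for the same potential drug-induced liver injury, and possible Hy's Law is defined and classified in two ways

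*Protocol*

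**What the plan says.** **Section 7.1.1.** Its criteria "require immediate and permanent discontinuation of IMP for study participants with either of the following": ALT or AST ≥8×ULN, or ALT or AST ≥3×ULN with total bilirubin ≥2×ULN. No exception is given for these two. Resumption under Section 10.6.2.1 is mentioned only for the group with ALT or AST ≥3×ULN and symptoms. For symptom-free ALT or AST of 5 to <8×ULN with bilirubin <2×ULN, IMP may continue at the investigator's discretion, "with repeat tests performed in 2 weeks". If the retest is below 5×ULN, the participant carries on. If it is still 5 to <8×ULN, IMP is withheld and the test repeated two weeks later. If it is then still ≥5×ULN, the participant is permanently withdrawn from the study and followed. Later in the same section, participants with PDILI "should not be withdrawn from the study until investigation and monitoring are complete".

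**Appendix 6.** Section 10.6 covers every IMP stop for PDILI under 7.1.1. The stop is permanent unless a later alternative diagnosis fully accounts for the liver findings; if it does, and Section 10.6.2.1 is satisfied, "rechallenge with IMP may be appropriate". Section 10.6.2.1 describes those who may restart as having met certain 7.1.1 criteria, does not list which, and sets eight requirements. For the 5 to <8×ULN group, Table 10-2 adds an entry condition of ≥2×Baseline. It asks sites to make every attempt to "have repeat liver chemistry values and additional testing completed within 48 hours" and to monitor at least twice weekly for two weeks, and it stops IMP if values go on rising. After a second retest ≥5×ULN it requires IMP discontinuation with continued monitoring.

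**Possible Hy's Law.** The Table 10-1 footnote (Section 10.2) takes ALT ≥3×ULN with bilirubin ≥2×ULN (>35% direct), or ALT ≥3×ULN with INR >1.5 if measured; such events "must be reported as an SAE". Section 8.2.8.6 takes ALT or AST ≥3×ULN with bilirubin ≥2×ULN, without ALP ≥2×ULN and without another explanation, and makes it an AESI. Section 10.6 repeats the AESI rule and adds, "if applicable, also reported as an SAE".

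**The concern.** Rules for stopping treatment should give one action for one set of laboratory values. Here the action depends on which part of the protocol a site has open.

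The first stake is participant safety and uniform conduct across sites. The analysis is touched as well. Discontinuation of IMP before Week 16 is the intercurrent event that makes a participant a nonresponder on both co-primary endpoints (Protocol 9.3.2, SAP 5.1.1.7), whereas a temporary hold is not stated to be one. TE-SAE incidence is a secondary endpoint, liver test changes are a prespecified safety topic, and potential Hy's Law is the only AESI listed.

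**Working it through.** No planned figure needs reproducing: no sample size, power or alpha value rests on these rules. The check takes typical cases through both texts.

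**Case 1, rising values below 8×ULN.** Suppose a symptom-free participant goes from 5.5×ULN to 7.5×ULN.
- 7.1.1: the value is still 5 to <8×ULN at the 2-week retest, so IMP is withheld and the test repeated two weeks later.
- Table 10-2: the values are increasing, so IMP discontinuation is required at once.
- Result: a hold under one text, a stop under the other.

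**Case 2, ALT ≥8×ULN with a proven non-drug cause.**
- 7.1.1: permanently off IMP.
- 10.6: the stop can be lifted if 10.6.2.1 is satisfied, and 10.6.2.1 does not say whether this group is among its eligible criteria.
- The same holds for ≥3×ULN with bilirubin ≥2×ULN.

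**Case 3, second retest ≥5×ULN.**
- 7.1.1, retest rule: withdrawn from the study.
- Table 10-2: IMP discontinued, monitoring continues.
- 7.1.1, later paragraph: no study withdrawal until the work-up is finished.
- IMP stops under all three, so nonresponder status is the same. What differs is study participation and therefore follow-up.

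**Case 4, possible Hy's Law.** Each of these meets one definition and not the other:
- AST ≥3×ULN with ALT below 3×ULN, bilirubin ≥2×ULN, no ALP rise, no other explanation: meets 8.2.8.6 only.
- ALT ≥3×ULN, bilirubin ≥2×ULN with >35% direct, ALP ≥2×ULN: meets the footnote only.
- ALT ≥3×ULN with INR >1.5 and bilirubin <2×ULN: meets the footnote only.

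Where both definitions are met, seriousness is mandatory in the footnote and conditional in 10.6.

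**Size for the analysis.** With 30 and 15 planned participants (Protocol 9.8), one responder reclassified as a nonresponder moves an arm's rate by 1/30 = 3.3 or 1/15 = 6.7 percentage points.

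**Lesser mismatches.**
- *Baseline condition.* The Table 10-2 entry value is max(5×ULN, 2×Baseline), against 5×ULN in 7.1.1. They differ only if 2×Baseline >5×ULN, that is, Baseline >2.5×ULN. Baseline 2.75 gives 5.5×ULN; 2.99 gives 5.98×ULN. Screening excludes ≥3×ULN, so the gap stays below 1×ULN unless values rise between Screening and Baseline (3.5 would give 7.0×ULN).
- *Within Table 10-2.* The 4-week stop in the Actions column carries the Baseline condition and a proviso about resolution; the corresponding stop in the Evaluation column carries neither.
- *Test timing.* In the first two weeks 7.1.1 implies at least one test, and Table 10-2 at least 2 × 2 = 4 (the 48-hour repeat may be one of them).

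**The case against.** **Timing.** A reader might infer that sites cannot follow both texts, or that the retest slips by 12 days (14 − 2). The documents do not support this. Section 7.1.1.1 sends follow-up monitoring to Table 10-2, the two texts share the 2-week decision and the second retest, and footnote e of the table allows another agreed schedule. A site that tests within 48 hours, twice weekly and again at two weeks satisfies both. A small residue stands: 7.1.1 requires an immediate IMP stop for anyone who cannot keep to the applicable monitoring schedule, so it should be plain which schedule applies.

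**Reporting.** A reader might also infer that 7.1.1 and Appendix 6 disagree on reporting. They do not: 7.1.1 has no AE, SAE or AESI rule, only source and eCRF documentation. The mismatch lies between the Table 10-1 footnote and Sections 8.2.8.6 and 10.6. Its effect is limited, because PDILI events and the AESI go to the sponsor within 24 hours anyway and Appendix 3 names potential Hy's Law as an event usually considered serious.

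**Rechallenge.** Section 10.6.2 defers to 7.1.1 for which stops are permanent. The eight requirements in 10.6.2.1 are strict, and they include having no alternative treatment. Its limits on ALT or AST (5×ULN) and bilirubin (2×ULN), if read as peak values, would close rechallenge to both permanent-stop groups. But 10.6.2.1 does not say whether it means peak or current values, and the sentence in 10.6 covers every PDILI stop. The conflict is narrow in practice and unresolved in the text.

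**Withdrawal.** The two statements in 7.1.1 can be read in sequence: withdraw, but only once the work-up is complete. That eases the tension inside 7.1.1 but not the difference from Table 10-2, which stops IMP and does not mention study withdrawal.

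**Conclusion.** The point holds as an inconsistency in current protocol text. Three conflicts lie between 7.1.1 and Appendix 6: whether the two most serious criteria can ever lead to rechallenge, what happens to values that rise but stay below 8×ULN, and whether a second high retest ends study participation or only IMP. A fourth, separate conflict concerns the definition and seriousness of possible Hy's Law. The timing and ≥2×Baseline differences are secondary.

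The likely effect on results is small. The documents give no event frequency, so the expected number of affected participants cannot be stated. The 3.3 and 6.7 percentage points assume the planned arm sizes and one participant who would otherwise respond. Of the three conflicts, the rising-values rule bears most directly on nonresponder status, because it sets a hold against a discontinuation. The case for correction rests mainly on safety conduct and uniformity across sites, and the correction is cheap.

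**What to change.** The sponsor must reconcile these passages. Keep the PDILI rules in one place, either Section 7.1.1 or Table 10-2, and have the other refer to it. For each criterion state:
- the thresholds, including whether the Baseline condition applies, and the retest schedule;
- what is done when values rise but stay below 8×ULN;
- whether the action concerns IMP or study participation;
- whether rechallenge is open, with the eligible criteria listed in 10.6.2.1 and its laboratory limits tied to a stated time.

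Use one definition of possible Hy's Law and one seriousness rule in Table 10-1, Section 8.2.8.6 and Section 10.6. SAP 5.6.3.1.1 and 6.1.6 use the same laboratory limits as 8.2.8.6, so they change only if the sponsor settles on something else.

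No view is given on which clinical rule is right. The cost is protocol wording; sample size and the planned efficacy analyses are unaffected.

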7.1.1.1 Follow-up evaluation

Potential drug-induced liver injury events require follow-up monitoring as described in Table 10-2. Monitoring should continue until liver chemistry values normalize, stabilize, or return to Baseline. Determination of stabilization is at the discretion of the Investigator in consultation with the hepatologist (as applicable) and UCB responsible physician, as needed.

7.1.2 Clinical laboratory criteria

Study participants should be monitored for absolute neutrophil count and/or absolute lymphocyte count as described in Section 7.1.

7.1.3 Treatment interruptions/temporary discontinuation of IMP

Doses of IMP that were missed due to a reasonable interfering AE or exceptional circumstance, which do not allow administration of IMP due to safety reasons, will not result in the study participant being considered noncompliant. The AE or exceptional circumstance should be discussed immediately with the Medical Monitor.

Any considerations related to restarting IMP should be discussed with the Medical Monitor.

The Investigator should not deviate from the protocol. However, the Investigator should take any measure necessary in deviation from, or not defined by, the protocol in order to protect clinical study participants from any immediate hazard to their health and safety. In this case, this action should be taken immediately, without prior notification of the regulatory authority, IRB/IEC, or Sponsor.

After implementation of such measure, the Investigator must notify the CPM of the Sponsor within 24 hours and follow any local regulatory requirements.

Any participant who develops a clinically important infection or recurrent infection not responsive to standard therapy during the study must discontinue IMP until resolution of the infection. The Investigator should use clinical judgement in deciding whether the participant should restart IMP, and contact the Medical Monitor and UCB study physician to confirm the participant's suitability for continued participation in the study.

7.2 Participant discontinuation/withdrawal from the study

If a study participant is unable to attend a visit due to the COVID-19 pandemic, study specific contingencies will be followed and the study participant should not be withdrawn.

Study participants are free to withdraw from the study at any time, without prejudice to their continued care.

Study participants should be withdrawn from the study and will be encouraged to come back for the SFU Visit 20 weeks after last dose of IMP if the study participant withdraws his/her consent or the Sponsor or a regulatory agency requests withdrawal of the study participant.

A study participant may withdraw from the study at any time at his/her own request, or may be withdrawn at any time at the discretion of the Investigator for safety, behavioral, compliance, or administrative reasons.

If the study participant withdraws consent for disclosure of future information, the Sponsor may retain and continue to use any data collected before such a withdrawal of consent.

If a study participant withdraws from the study, he/she may request destruction of any samples taken and not tested, and the Investigator must document this in the site study records.

See the SoA for data to be collected at the time of study discontinuation, follow-up, and any further evaluations that need to be completed (Table 1-1).

Refer to Section 7.1 for additional participant discontinuation/withdrawal criteria.

7.3 Lost to follow up

A study participant will be considered lost to follow-up if he or she repeatedly fails to return for scheduled visits and is unable to be contacted by the study site.

The following actions must be taken if a study participant fails to return to the clinic for a required study visit:

- The site must attempt to contact the study participant and reschedule the missed visit as soon as possible, counsel the study participant on the importance of maintaining the assigned visit schedule, and ascertain whether or not the study participant wishes to and/or should continue in the study.
- Before a study participant is deemed lost to follow up, the Investigator or designee must make every effort to regain contact with the study participant (at least 1 phone call and 1 written message to the study participant), and document his/her effort (date and summary of the phone call and copy of the written message in the source documents) to complete the final evaluation. All results of these evaluations and observations, together with a narrative

description of the reason(s) for removing the study participant, must be recorded in the source documents. The eCRF must document the primary reason for withdrawal.

Should the study participant continue to be unreachable, he/she will be considered to have withdrawn from the study with a primary reason of lost to follow up documented in the eCRF.

8 STUDY ASSESSMENTS AND PROCEDURES

Study procedures and their timing are summarized in the SoA ([Table 1-1](#)).

Some study-specific investigations may not be possible to be conducted according to the study protocol during a pandemic or other exceptional circumstances (eg, hurricanes) due to the need to implement safety measures and guidance from regulatory authorities. In such a situation, which may be accompanied by local or global containment or other measures, sites may need to prohibit access to study participants and study-related personnel. Study participants' visits to the study site may be replaced by contingency measures. These measures are primarily established to ensure the continued safety of study participants during the course of the study and to maintain the study participants' treatment schedule; if the Investigator considers it appropriate. The contingency measures will be described in a contingency plan which will be maintained by UCB for the respective study. The contingency measures are shared with the Investigator and the respective study-related personnel as soon as there are indications that it is necessary to implement any of the measures.

Protocol waivers or exemptions are not allowed.

Immediate safety concerns should be discussed with the Sponsor immediately upon occurrence or awareness to determine if the study participant should continue or discontinue IMP.

Adherence to the study design requirements, including those specified in the SoA, is essential and required for study conduct.

All screening evaluations must be completed and reviewed to confirm that potential study participants meet all eligibility criteria at the Baseline Visit for randomization. The Investigator will maintain a screening log to record details of all participants screened and to confirm eligibility or record reasons for screening failure, as applicable.

Procedures conducted as part of the study participant's routine clinical management (eg, blood count) and obtained before signing of the ICF may be utilized for Screening or Baseline purposes provided the procedures met the protocol-specified criteria and were performed within the time frame defined in the SoA ([Table 1-1](#)).

Repeat or unscheduled samples may be taken for safety reasons or for technical issues with the samples.

